APPENDIX A: Life Story Questionnaire

Professional Care Partners: Use this questionnaire to learn about the clients you work with. Complete one questionnaire with each client and/ or the client's loved ones. This great resource will provide you with helpful information as you get to know your clients and encourage their interests and abilities.

Family Care Partners: Use this questionnaire to help others learn about your loved one. Complete this questionnaire with your family member or on her behalf. With this valuable tool in hand, everyone who cares for your loved one will have the information they need to engage her likes and interests.

Background:

Full name _____

Does your name have a special significance?

Do you have a nickname?

Where did your nickname come from?

Where were you born?

What was your father's name?

Please describe your father.

What was your mother's name?

Please describe your mother.

Do you have brothers and/or sisters?

If yes, please describe your siblings.

Did you know your grandparents?

If yes, please describe your grandparents.

Where did you grow up?

Please describe the house you lived in.

What was your neighborhood like?

Who were your neighbors?

What games did you play?

Are/were you married?

If yes, please describe your spouse.

you have children and grandchildren?

If yes, please describe your children and grandchildren.

Daily Routine

What time do you like to get up in the morning?

Do you prefer to stay in your pajamas for a while?

Describe your routine after waking (e.g., brushing your teeth, doing your hair, dressing).

Do you prefer showers or baths?

At what time of day do you take a shower/bath?

Do you eat breakfast?

If yes, what do you like to eat for breakfast?

What's your typical lunch and afternoon routine?

Do you like to take naps?

Do you like a big meal at noon or in the evening?

Please describe your typical evening routine.

What time do you like to go to bed?

What hygiene products do you prefer?

Education Where did you go to school?

How did you get there?

What did you like about school?

Also ask questions about high school and college, if appropriate.

Work

What was your first paid job?

What kind of job was it?

What were your duties/responsibilities?

What were your accomplishments?

Leisure

What are your hobbies/interests?

What are your favorite movies/books?

Do you enjoy music? If yes, what kind?

Did you have pets? If so, what kind, and what were their names?

Are you afraid of or allergic to any pets?

Did you travel, and if so, where did you go?

What have been some special events in your life?

What's your favorite time of year?

Do you prefer solitary activities, small groups, or large groups?

Religion/Faith

Did you attend a place of worship?

Did you have a role in the services? If so, please describe.

How did you spend your day of worship?

Do you have a prayer book?

Emotional Needs What makes you feel happy?

What makes you feel safe?

What makes you feel sad?

Is there anything that helps you alleviate this feeling?

What makes you feel anxious, angry, or frustrated?

Is there anything that helps you alleviate these feelings?

Please describe your bedroom at home.

Please describe the room in your home where you relaxed.

Additional Information

Please note other important likes and interests.

APPENDIX B: PITTSBURGH REHABILITATION PARTICIPATION SCALE

Patient name: _____

Date: _____

Instructions to therapist: for each therapy session, please circle one of each of the following to assess the patient’s participation (effort and motivation as perceived by you) in the therapy session.

Please rate as follows:

None: patient refused entire session, or did not participate in any exercises in session. (see Note below)

Poor: patient refused or did not participate in at least half of session. **Fair:** patient participated in most or all of exercises*, but did not show maximal effort or finish most exercises*, or required much encouragement to finish exercises*.

Good: patient participated in all exercises* with good effort and finished most but not all exercises* and passively followed directions (rather than actively taking interest in exercises* and future therapy).

Very good: patient participated in all exercises* with maximal effort and finished all exercises, but passively followed directions (rather than actively taking interest in exercises* and future therapy).

Excellent: patient participated in all exercises* with maximal effort, finished all exercises*, and actively took interest in exercises* and/or future therapy sessions.

Note: if patient was unable to attend therapy because of medical test, bed rest order, illness, or scheduling conflict, do not mark any score. Note: in cases of doubt, choose the lower rating, eg, “good” rather than “very good.”

Participation:

Session Number	Date	Therapist Initials	None	Poor	Fair	Good	Very good	Excellent
1 – prior to intervention			1	2	3	4	5	6
2 – 3-week			1	2	3	4	5	6
3 – 6-week			1	2	3	4	5	6
4 – 6-week following end intervention			1	2	3	4	5	6

* This version is specifically for physical therapists. For the occupational therapy form, “exercises” should be replaced by “activities”.

Source: <https://www.sralab.org/sites/default/files/2017-06/PITTSBURGH%20REHABILITATION%20PARTICIPATION%20SCALE.pdf>

APPENDIX C: Quality of Life in Alzheimer's Disease Instruction for interviewers

The Quality of Life in Alzheimer's Disease (QOL-AD) is administered in interview format to individuals with dementia, following the instructions below. The interview is carried out with the subject and/or an informant. The subject should be interviewed alone. Hand the form to the participant, so that he or she may look at it as you give the following instructions (instructions should closely follow the wording given in bold type): **I want to ask you some questions about your quality of life and have you rate different aspects of your life using one of four words: poor, fair, good, or excellent.** Point to each word (poor, fair, good, and excellent) on the form as you say it. When you think about your life, there are different aspects, like your physical health, energy, family, money, and others. I'm going to ask you to rate each of these areas. We want to find out how you feel about your current situation in each area. If you're not sure about what a question means, you can ask me about it. If you have difficulty rating any item, just give it your best guess. It is usually apparent whether an individual understands the questions, and most individuals who are able to communicate and respond to simple questions can understand the measure. If the participant answers all questions the same, or says something that indicates a lack of understanding, the interviewer is encouraged to clarify the question. However, under no circumstances should the interviewer suggest a specific response. Each of the four possible responses should be presented, and the participant should pick one of the four. If a participant is unable to choose a response to a particular item or items, this should be noted in the comments. If the participant is unable to comprehend and/or respond to two or more items, the testing may be discontinued, and this should be noted in the comments. As you read the items listed below, ask the participant to circle her/his response. If the participant has difficulty circling the word, you may ask her/him to point to the word or say the word, and you may circle it for him or her. You should let the participant hold his or her own copy of the measure, and follow along as you read each item.

1. **First of all, how do you feel about your physical health?** Would you say it's poor, fair, good, or excellent? Circle whichever word you think best describes your physical health right now.
2. **How do you feel about your energy level?** Do you think it is poor, fair, good, or excellent? If the participant says that some days are better than others, ask him or her to rate how she/he has been feeling most of the time lately.
3. **How has your mood been lately?** Have your spirits been good, or have you been feeling down? Would you rate your mood as poor, fair, good, or excellent?
4. **How about your living situation?** How do you feel about the place you live now? Would you say it's poor, fair, good, or excellent?
5. **How about your memory?** Would you say it is poor, fair, good, or excellent?

6. **How about your family and your relationship with family members?**
Would you describe it as poor, fair, good, or excellent? If the respondent says they have no family, ask about brothers, sisters, children, nieces, nephews.
7. **How do you feel about your marriage?** How is your relationship with (spouse’s name). Do you feel it’s poor, fair, good, or excellent? Some participants will be single, widowed, or divorced. When this is the case, ask how they feel about the person with whom they have the closest relationship, whether it’s a family member or friend. If there is a family caregiver, ask about their relationship with this person. If there is no one appropriate, or the participant is unsure, score the item as missing.
8. **How would you describe your current relationship with your friends?**
Would you say it’s poor, fair, good, or excellent? If the respondent answers that they have no friends, or all their friends have died, probe further. Do you have anyone you enjoy being with besides your family? Would you call that person a friend? If the respondent still says they have no friends, ask how do you feel about having no friends—poor, fair, good, or excellent?
9. **How do you feel about yourself?** —when you think of your whole self, and all the different things about you, would you say it’s poor, fair, good, or excellent?
10. **How do you feel about your ability to do things like chores around the house or other things you need to do?** Would you say it’s poor, fair, good, or excellent?
11. **How about your ability to do things for fun, that you enjoy?** Would you say it’s poor, fair, good, or excellent?
12. **How do you feel about your current situation with money, your financial situation?** Do you feel it’s poor, fair, good, or excellent? If the respondent hesitates, explain that you don’t want to know what their situation is (as in amount of money), just how they feel about it.
13. **How would you describe your life as a whole?** When you think about your life as a whole, everything together, how do you feel about your life? Would you say it’s poor, fair, good, or excellent?

Scoring instructions for QOL-AD:

Points are assigned to each item as follows: poor = 1, fair = 2, good = 3, excellent = 4. The total score is the sum of all 13 items.

Participant Last Name: _____ **First Name:** _____

Date: __/__/202__

QOL: Alzheimer Disease (Participant’s version)

Instruction:					Score
1. Physical health	Poor	Fair	Good	Excellent	

Dementia - Life Story Questionnaire – Physical Therapy

2. Energy	Poor	Fair	Good	Excellent	
3. Mood	Poor	Fair	Good	Excellent	
4. Living situation	Poor	Fair	Good	Excellent	
5. Memory	Poor	Fair	Good	Excellent	
6. Family	Poor	Fair	Good	Excellent	
7. Marriage	Poor	Fair	Good	Excellent	
8. Friends	Poor	Fair	Good	Excellent	
9. Self as a whole	Poor	Fair	Good	Excellent	
10. Ability to do chores around the house	Poor	Fair	Good	Excellent	
11. Ability to do things for fun	Poor	Fair	Good	Excellent	
12. Money	Poor	Fair	Good	Excellent	
13. Life as a whole	Poor	Fair	Good	Excellent	
Comments:					

Source: <https://www.cogsclub.org.uk/professionals/files/QOL-AD.pdf>

APPENDIXE D: Cornell Scale for Depression in Dementia

The scale is designed as a screening tool and is not diagnostic.

The Cornell Scale for Depression in Dementia (CSDD) was specifically developed to assess signs and symptoms of major depression in demented patients. Because some of these patients may give unreliable reports, the CSDD uses a comprehensive interviewing approach that derives information from the patient and the informant. Information is elicited through two semi-structured interviews; an interview of an informant and an interview of the patient. The interviewer should assign preliminary scores to each item of the scale on the basis of the informant's report in the "Informant" column. The next step is for the rater to interview the patient using the Cornell scale items as a guide. The interviews focus on depressive symptoms and signs occurring during the week preceding the interview. Many of the items during the patient interview can be filled after direct observation of the patient. If there are discrepancies in ratings from the informant and the patient interviews, the rater should re-interview both the informant and the patient with the goal to resolve the discrepancies. The final ratings of the CSDD items represent the rater's clinical impression rather than the responses of the informant or the patient. The CSDD takes approximately 20 minutes to administer.

Cornell Scale for Depression in Dementia

Participant Last Name: _____ First Name: _____

Date: __/__/202__

Scoring System:

- a = unable to evaluate 0
- = absent
- 1= mild or intermittent
- 2 = severe

Ratings should be based on symptoms and signs occurring during the week prior to interview. No score should be given if symptoms result from physical disability or illness.

A. Mood-Related Signs

- | | | | | |
|---|---|---|---|-------|
| 1. Anxiety | a | 0 | 1 | 2 |
| anxious expression, ruminations, worrying | | | | |
| 2. Sadness | a | 0 | 1 | 2 sad |
| expression, sad voice, tearfulness | | | | |
| 3. Lack of reactivity to pleasant events | a | 0 | 1 | 2 4. |
| Irritability | a | 0 | 1 | 2 |
| easily annoyed, short-tempered | | | | |

B. Behavioral Disturbance

- | | | | | |
|--|---|---|---|--------|
| 1. Agitation | a | 0 | 1 | 2 |
| restlessness, handwringing, hairpulling | | | | |
| 2. Retardation | a | 0 | 1 | 2 |
| slow movements, slow speech, slow reactions | | | | |
| 3. Multiple physical complaints | a | 0 | 1 | 2 |
| 4. Loss of interest | a | 0 | 1 | 2 less |
| involved in usual activities (score only if change occurred acutely, i.e.in less than 1 month) | | | | |

C. Physical Signs

- | | | | | |
|--|---|---|---|---|
| 1. Appetite loss | a | 0 | 1 | 2 |
| eating less than usual | | | | |
| 2. Weight loss | a | 0 | 1 | 2 |
| score 2 if greater than 5 lb. in one month | | | | |
| 3. Lack of energy | a | 0 | 1 | 2 |
| fatigues easily, unable to sustain activities (score only if change occurred acutely, i.e., in less than 1 month) continued on reverse | | | | |

D. Cyclic Functions

- | | | | | |
|-------------------------------|---|---|---|---|
| 1. Diurnal variation of mood | a | 0 | 1 | 2 |
| symptoms worse in the morning | | | | |

Dementia - Life Story Questionnaire – Physical Therapy

- | | | | | |
|--|---|---|---|---|
| 2. Difficulty falling asleep
later than usual for this individual | a | 0 | 1 | 2 |
| 3. Multiple awakenings during sleep | a | 0 | 1 | 2 |
| 4. Early-morning awakening
earlier than usual for this individual | a | 0 | 1 | 2 |

E. Ideational Disturbance

- | | | | | |
|--|---|---|---|---|
| 1. Suicide
feels life is not worth living, has suicidal wishes or makes suicide attempt | a | 0 | 1 | 2 |
| 2. Poor self-esteem
self-blame, self-depreciation, feelings of failure | a | 0 | 1 | 2 |
| 3. Pessimism
2 anticipation of the worst | a | 0 | 1 | 1 |
| 4. Mood-congruent delusions
2 delusions of poverty, illness or loss | a | 0 | 1 | 1 |

Scoring: A score >10 probably major depressive episode

A score >18 definite major depressive episode

Source:

<https://dementiaresearch.org.au/wp-content/uploads/2016/06/CSDD.pdf>

APPENDIX E: Mini-Mental State Examination

Patient's Name: _____ **Date:** __/__/202__

Instruction: Ask the questions in the order listed. Score one point for each correct response within each question or activity.

Maximum score	Patient's Score	Questions
5		"What is the year? Season? Date? Day of the week? Month?"
5		"Where are now: state? Country? Town/city? Hospital? Floor?"
3		The examiner names three unrelated objects clearly and slowly, then asks the patient to name all three of them. The patient's response is used for scoring. The examiner repeats then until patient learns all of them, if possible. Number of trials:
5		"I would like you to count backward from 10- by sevens." (93,86,79,72, 65...) stop after five answers. Alternative: "spell WORLD backwards." (D-L-R-O-W)
3		"Earlier I told you the names of three things. Can you tell me what those were?"
2		Show the patient two simple objects, such as a wristwatch and a pencil, and ask the patient to name them.
1		"Repeat the phrase: No ifs, ands, or buts."
3		Take the paper in your right hand, fold it in half, and put it on the floor." (the examiner gives the patient a piece of blank paper.)
1		"Please read this and do what it says." (This sentence must contain a noun and a verb.)
1		"Please copy this picture." (The examiner gives the patient a blank piece of paper and asks him/her to draw the symbol below. All 10 angles must be present and two must intersect.) 
30		Total

Interpretation of MMSE Scores:

Score	Degree of Impairment	Formal Psychometric Assessment	Day-to-Day Functioning
24-30	Questionably significant	If clinical signs of cognitive impairment are present, formal assessment of cognition may be valuable.	May have clinically significant but mild deficits. Likely to affect only most demanding activities of daily living
19-23	Mild	Formal assessment may be helpful to better determine pattern and extent of deficits.	Significant effect. May require some supervision, support and assistance.
10-18	Moderate	Formal assessment may be helpful if there are specific clinical indications.	Clear impairment. May require 24hour supervision.
0-9	Severe	Patient not likely to be testable	Marked impairment. Likely to require 24-hour supervision and assistance with ADL.

Source:

Adapted from Folstein MF, Folstein SE, McHugh PR: "Mini-mental state: A practical method for grading the cognitive state of patients for the clinician." J Psychiatr Res 1975;12:189-198

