Power calculations were performed to determine the sample size required for the study using the Pittsburgh participation in rehabilitation scale as the primary outcome measure and calculations using Mann-Whitney U test. The study was designed with α value set at 0.05 and Power set at 0.8 (β set at 0.2). The effect size was calculated using G*Power (version 3.1) using differences in the Pittsburgh participation in rehabilitation scale between the experimental versus the control group of 0.5 with a standard deviation of 0.5, based on pilot testing conducted at Peachtree Place, which resulted in effect size of 1 and a sample size of 44 (22 participants in each group) (<http://www.gpower.hhu.de/>).

Sampling

A consecutive sample of convenience of up to 60 patients (44 patients = 22 per group completing the study) with MMSE scale score between 10-18 (moderate cognitive impairment) and 19-23 (mild cognitive impairment), and residing at the Peachtree Place dementia care facility in Weatherford Texas will

be recruited. Patients (or their families) will be asked to participate after explanation of the study.

Subjects

Inclusion Criteria: (1) Patients residing in Peachtree Place in Weatherford, Texas; (2) Age 60-89 years; (2) Diagnosis of dementia disease, in mild to moderate stage using the MMSE (score between 10-23)^{22,23} and (3) attendance to physical therapy for 6 weeks.

Exclusion Criteria: (1) Unable to speak English; (2) blindness; (3) deafness; (4) MMSE score >23 and (5) history of major psychiatric disorder such as schizophrenia and bipolar disorder that required hospital admission within the last year.

Sequence

Reliability Testing

Investigator 2, who is a licensed occupational therapist with 15 years of clinical experience in geriatric population care, will be educated to collect the three dependent variables including the Pittsburg Rehabilitation Participation scale, the quality of life -Alzheimer's disease scale and the Cornell Scale of Depression in Dementia (CSDD) scale to establish intra-rater reliability.

Investigator 1 who is the principal investigator and a licensed physical therapist with 10-year experience treating geriatric population and has experience in using the Pittsburg Rehabilitation Participation scale, the quality of life -Alzheimer's disease scale and the CSDD scale, will explain and educate Investigator 2 in

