each scale usage. After demonstration, Investigator 2 will record the three dependent variables measurements on the same patients twice, with at least 48hour interval between measurements. A minimum of five patients will be used. The intra-rater reliability of measurements on the two separate days will be calculated.

Study Sequence

Investigator 1 will conduct patients' screening (Appendix F) before they enroll the study to determine their eligibility. Participants with mild cognitive impairment (MMSE 19-23) demonstrating understanding of the research and the consent decision and indicating a willingness to take part will be asked to sign a consent form. For participants with moderate cognitive impairment (MMSE 10-18), both the potential participants and their legally authorized representatives will be asked to give consent to allow study participation.

Patients will be randomly assigned using block randomization with a 1:1 allocation ratio and randomly permuted block sizes of 2 to 6 based on severity of cognitive impairment. The randomization will be performed in R software (version 4.1.2, R Core Team) using the randomize R package (version 2.0). Each subject will be randomized to one of two interventions: (1) Control group, which will receive standard physical therapy care without LSQ use; and (2) Experimental group, where physical therapists will use the LSQ. The randomization file will be generated by Investigator 1 (Physical therapist) not involved in the data collection process, with the results stored in a spreadsheet accessible only to the investigator responsible for the subjects' group assignment. This investigator will

not participate in any data collection. Due to the nature of the study, participants will not be blinded to the group assignment and to the treatment they will receive. Investigator 2 measuring the dependent variables, however, will be blinded to the group assignment.

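### The MMSE item maxima in Appendix E add to 29, not the printed 30; a 1-point item appears to be missing, which changes a patient's category only at scores of 10, 19 and 24

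*Combined protocol and SAP*

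**What the plan says.** Appendix E is the form on which the MMSE is scored. Its instruction is "Score one point for each correct response within each question or activity", so the total is the sum of the row scores. It has ten scored rows, a total row showing 30, and an interpretation table with bands 0-9, 10-18, 19-23 and 24-30. The ninth row, worth 1 point, is a read-and-obey prompt, and its note reads "This sentence must contain a noun and a verb".

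The score is used in four places:

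- **Eligibility** (Subjects): dementia "in mild to moderate stage using the MMSE (score between 10-23"; a score above 23 is an exclusion.
- **Randomisation** (Study Sequence): permuted blocks "based on severity of cognitive impairment". The severity bands, 10-18 moderate and 19-23 mild, are given under Sampling.
- **Consent** (Study Sequence): patients scoring 19-23 sign for themselves. "For participants with moderate cognitive impairment (MMSE 10-18"), the patient and a legally authorised representative are both asked.
- **Research Question 4** (Data Analysis): the MMSE is correlated with the participation scale by Spearman's method.

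**The concern.** Every cut-off in the protocol (10, 18/19, 23) is read off a 30-point scale. A form that can reach only 29 scores some patients one point too low against those cut-offs. Near a boundary, that point can decide whether a patient enters the trial, which severity band applies at randomisation, and whether a representative must also consent.

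The note in the ninth row suggests where the point went. It reads as a scoring rule for something the patient composes, but it sits beside a prompt to read and obey, and nothing else on the form asks for a sentence.

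**Working it through.** **Step 1: try to reproduce the printed total of 30.** All inputs are from Appendix E.

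| Row | Task | Responses asked for | Printed maximum | Running sum |
|---|---|---|---|---|
| 1 | Time ("What is the year? Season? Date? Day of the week? Month") | 5 | 5 | 5 |
| 2 | Place ("Where are now: state? Country? Town/city? Hospital? Floor") | 5 | 5 | 10 |
| 3 | Registration ("The examiner names three unrelated objects clearly and slowly") | 3 | 3 | 13 |
| 4 | Serial sevens or backward spelling | 5 | 5 | 18 |
| 5 | Recall | 3 | 3 | 21 |
| 6 | Naming | 2 | 2 | 23 |
| 7 | Repetition | 1 | 1 | 24 |
| 8 | Three-stage command | 3 | 3 | 27 |
| 9 | Reading prompt with the sentence note | 1 | 1 | 28 |
| 10 | Copying | 1 | 1 | 29 |

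The sum is 29, so the printed 30 is not reproduced; the gap is 30 − 29 = 1. Each maximum equals the number of responses its row asks for, so recounting a row does not recover the point.

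**Step 2: test the likely explanation.** If row 9 holds the start of one 1-point item and the end of another, separating them gives 29 + 1 = 30, which matches the total row and the top interpretation band.

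**Step 3: find where one point matters.** Let s be the score on a complete 30-point form and s − 1 the score on the printed form for a patient who would have earned the missing point. Apply the bands below 10 (not eligible), 10-18 (moderate), 19-23 (mild) and above 23 (excluded) to every s from 1 to 30. The band changes at exactly three values:

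- s = 10 becomes 9: eligible becomes below range.
- s = 19 becomes 18: mild becomes moderate, and representative consent is added.
- s = 24 becomes 23: excluded becomes within the MMSE range.

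At every other score the lost point changes nothing in eligibility, band or consent route. This step uses the 10-23 range in the inclusion criteria and in the office section of Appendix F; question 2 of Appendix F words the lower limit as above 10.

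**Step 4: effect on the analyses.** Screening comes before enrolment and allocation, so the error cannot depend on the assigned group. For Research Question 4, take two patients with full-form scores a > b. Each loses 0 or 1 point, so their order can become a tie (when a = b + 1) but cannot reverse; equal scores can separate by one point. Spearman ranks therefore barely move.

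**Step 5: serial sevens.** The listed answers start at 93 and fall by 7, which implies a start of 93 + 7 = 100. The form as read shows 10 followed by a hyphen; a start of 10 would give 10 − 7 = 3.

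**The case against.** The strongest objection is that the fault may lie in the PDF reading and not in the form. The neighbouring Cornell scale in Appendix D shows broken rows, and losing one stretch of text between two adjacent 1-point rows would leave just this pattern: the start of one row joined to the end of the next, and a sum one short. The printed 30 fits an intact original as well as it fits a typing error. The serial-sevens start could likewise be a misread 100, and the listed answers already show a rater where to begin.

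This stands in part: the text alone cannot settle the cause. A retyped form is still the more likely one. The same form has other slips of a typing kind, such as a missing word in the place prompt and a wrong word in the registration instructions. Checking the original page decides the matter.

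A second objection is that a separate sentence-writing item is only an inference from a stray note, which might be meant for the sentence shown to the patient. That is fair, and it is why the source instrument should be consulted before a row is added. The mismatch of 29 and 30 does not depend on how the note is read.

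A third objection concerns the consequences, and it largely stands. At 19 to 18 the patient is still asked and a representative is added, so no consent safeguard is lost. At 24 to 23 the patient must still meet the other criteria, including a dementia diagnosis. The randomisation text does not itself state an 18/19 cut-off; that comes from the bands under Sampling. A shifted band boundary leaves the randomisation valid.

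**Conclusion.** The form as printed contradicts its own total by one point, and the bands the protocol relies on are those of the 30-point scale. If the form is used as printed, the error is at most one point per patient. It falls only on patients who would have earned the missing point, and it has consequences only at full-form scores of 10, 19 and 24. This rests on two assumptions: that the printed page matches the extracted text, and that the missing point belongs to an omitted item.

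A reader might go further in two ways that the documents do not support:

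- **A misclassification rate.** Two of the 14 scores from 10 to 23 are exposed (2/14 = 14.3%), and if 50-90% of patients would earn the point this gives about 7-13%. But the documents give neither the distribution of scores nor any earning rate. A single rate for patients scoring 10 and 19 is implausible, and the exposed score of 24 lies outside the denominator. The number affected cannot be estimated.
- **A biased trial result.** The MMSE is taken before allocation, so the group comparison is not biased, and the Research Question 4 ranks are almost unchanged.

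What remains is a screening form that can misplace patients at three scores, worth correcting because the remedy is so small.

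**What to change.** Before screening, check Appendix E against the original page and against the source instrument. If the omission is confirmed, print the missing 1-point item as its own row, with its own prompt and note, so that the maxima add to 30. Make the serial-sevens starting number agree with the listed answers (93, 86, and so on).

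The protocol's timeline puts data collection from May 2023 to September 2024, so screening may already have begun. If so, record which form was used and re-check patients scored 9, 18 or 23 on the printed form, the values at which a lost point would have changed the category.

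The cost is the correction of one form and, if screening has started, a review of the records at those three scores. No change to the design, sample size or analysis is needed.
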